## 9. Statistical Analysis Plan (SAP)

### 9.1 General Analytical Principles

This Statistical Analysis Plan is finalised prior to completion of data collection for the intervention group. Analyses will be conducted according to the intention-to-treat principle, whereby all participants are analysed in the group to which they were allocated based on study phase, regardless of intervention adherence.

Given the feasibility nature of the study, analyses are primarily descriptive and exploratory. Formal hypothesis testing is not the primary objective. All statistical tests, where performed, will be two-sided with a nominal significance level of

0.05. Emphasis will be placed on estimation, confidence intervals, and clinical plausibility rather than statistical significance alone.

## 9.2 Analysis of Feasibility Outcomes

Recruitment will be calculated as the proportion of eligible women diagnosed with GDM who consent to participate in the study. Retention will be calculated as the proportion of enrolled women who provide delivery data and complete the postpartum questionnaire. Both outcomes will be presented as percentages with corresponding 95% confidence intervals.

Acceptability will be analysed using a mixed-methods approach. Quantitative acceptability scores will be summarised using means, standard deviations, medians, and ranges. The predefined progression criterion is a mean Likert score greater than 3. Qualitative data from ethnographic interviews will be analysed thematically to explore participants' experiences, perceived usefulness, and barriers to engagement with the intervention.

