## 8. Outcome Measures

The primary outcomes relate to feasibility:

- Recruitment is defined as the proportion of eligible women who consent to participate.
- Retention is defined as the proportion of enrolled women who complete delivery and postpartum follow-up.
- Acceptability is assessed using both quantitative Likert-scale measures and qualitative ethnographic interviews.

Secondary outcomes include maternal outcomes (e.g., self-care agency, perceived social support, gestational weight gain, HbA1c, breastfeeding practices, postpartum depression) and neonatal outcomes (e.g., birth weight, gestational age, large for gestational age, macrosomia, neonatal hypoglycaemia).

All outcomes and measurement tools are predefined and aligned with the published protocol .

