### 9.5 Missing Data

The extent and patterns of missing data will be described for all outcomes. Given the feasibility focus of the study, no formal imputation of missing data is planned. Analyses will be based on available data, and the potential impact of missingness will be discussed qualitatively.

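### Does the acceptability criterion (mean Likert above 3) need a prespecified confidence interval and a numerical check for non-response?

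*Combined protocol and SAP*

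**What the plan says.** Acceptability is one of three primary feasibility outcomes (section 8), assessed with Likert measures and ethnographic interviews. In section 9.2:

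- On the numerical summaries: "Quantitative acceptability scores will be summarised using means, standard deviations, medians, and ranges".
- On the threshold: "The predefined progression criterion is a mean Likert score greater than 3".
- On recruitment and retention, but not acceptability: "Both outcomes will be presented as percentages with corresponding 95% confidence intervals".
- On retention: "Retention will be calculated as the proportion of enrolled women who provide delivery data and complete the postpartum questionnaire".

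Section 9.1 states a principle for the whole analysis: "Emphasis will be placed on estimation, confidence intervals, and clinical plausibility rather than statistical significance alone". Section 9.5 plans no imputation because of the feasibility focus, and adds two commitments: "The extent and patterns of missing data will be described for all outcomes" and "Analyses will be based on available data, and the potential impact of missingness will be discussed qualitatively".

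The number of scale points, the timing of the acceptability measure, the sample size and the expected response rate do not appear in these documents. Section 8 refers the reader elsewhere for the instruments: "All outcomes and measurement tools are predefined and aligned with the published protocol".

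**The concern.** The study exists to prepare a randomised trial, and this is the only progression threshold with a number attached. As written, it is applied to a point estimate from the women who answered. The interval that would show how firmly the mean sits above 3 is specified for the other two feasibility outcomes and not for this one.

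Retention does not stand in for the acceptability response rate. Its denominator is enrolled women with no arm stated, and it requires delivery data plus the postpartum questionnaire. If women who disliked the intervention were less likely to reply, the observed mean would overstate acceptability, and a verbal discussion would not show by how much. At stake is a favourable reading of acceptability that a modest shift among non-responders would undo.

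**Working it through.** The documents contain no figure to reproduce: the threshold of 3 is the only number given. Every sample size, SD, response rate and scale below is an assumption.

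**Precision.** The 95% interval is m ± t(0.975, n−1) × SD/√n, where m is the responder mean and n the number responding. The half-width is:

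- 0.373 SD at n = 30
- 0.284 SD at n = 50
- 0.198 SD at n = 100

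With SD 1.0, the lower limit exceeds 3 only when the observed mean is above about 3.37, 3.28 or 3.20 respectively. Section 9.2 already commits to the mean and SD, and the number responding comes with the description of missing data under section 9.5. The interval is therefore recoverable.

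Reporting the interval would leave the rule's behaviour as it is. By the normal approximation with SD 1.0, a true mean of 2.9 gives an observed mean above 3 about 29% of the time at n = 30 and 16% at n = 100. Those rates are the same whether or not an interval is printed, because the criterion stays on the point estimate.

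**Non-response.** Let r be the response rate and s the mean score that non-responders would have given.

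- Mean over all women allocated to the intervention = r × m + (1 − r) × s.
- Setting this to 3 gives the tipping score s* = (3 − r × m)/(1 − r).
- The gap between responders and non-responders at that point is m − s* = (m − 3)/(1 − r).

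Tipping score s*:

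| Responder mean m | r = 0.9 | r = 0.8 | r = 0.7 | r = 0.6 |
|---|---|---|---|---|
| 3.2 | 1.20 | 2.20 | 2.53 | 2.70 |
| 3.4 | −0.60 | 1.40 | 2.07 | 2.40 |
| 4.0 | −6.00 | −1.00 | 0.67 | 1.50 |

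On an assumed 1–5 scale, any value below 1 is impossible, so the mean cannot be brought down to 3 in those cells. Worked examples at r = 0.7:

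- m = 3.2: s* = (3 − 2.24)/0.3 = 2.53, a gap of 0.67 points.
- m = 3.4 with non-responders averaging 2: 0.7 × 3.4 + 0.3 × 2 = 2.98, just below the threshold.
- m = 4.0 with every non-responder scoring 1: 0.7 × 4.0 + 0.3 × 1 = 3.10, still above it.

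The responder mean beyond which no score on a scale starting at 1 can reverse the result is (3 − (1 − r))/r, which is 3.22, 3.50, 3.86 and 4.33 at r = 0.9, 0.8, 0.7 and 0.6.

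**Reading.** The check bites only when three things coincide: a mean near the threshold, appreciable non-response, and non-responders who would have scored clearly lower. The documents supply no evidence on any of the three. The tipping score needs only m and r, which the planned summaries and the missing-data description should provide.

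**The case for a change.** The case for amending the plan is respectable. Acceptability is a primary outcome, yet even the exploratory comparisons in section 9.3 are given 95% intervals. Section 9.1 commits to analysing everyone as allocated, while the threshold will be read from responders only. Describing the extent of missing data does not show whether the criterion survives it. A check chosen after the mean is known carries less weight than one fixed beforehand, and the cost is a short dated addendum with no new data. At 70% response and a mean of 3.2, a gap of 0.67 points would be enough to bring the all-allocated mean down to 3.

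Some of this stands. Section 9.2 does omit the interval, retention is a poor proxy for the response rate, and the scale range cannot be read from these documents, although the published protocol may state it.

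The rest does not amount to a fault in the plan. The section 9.1 principle already covers a primary outcome mean, so an analyst following it would report the interval. Section 9.5 gives a reason for its approach and does not bar numbers from the discussion. The all-allocated mean is itself debatable: it assigns a score to women who may never have used the intervention or who left for unrelated reasons, so the tipping score is a bound and not an estimate. Nothing says the mean alone triggers progression. The interviews, which are to explore barriers to engagement, and retention with its own interval will be read beside it.

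**Conclusion.** No change to the plan is needed. The omission is a reporting detail that a competent analyst would fill from section 9.1, combined with a preference for a numerical over a qualitative account of missing answers. Followed as written, the plan produces no wrong estimate and no wrong rule. The mean, the threshold and the result of applying one to the other would be identical with the extra items.

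The possible effect ranges from none (a mean of 4.0 at 70% response or better, on an assumed 1–5 scale) to decisive (a mean of 3.2 at 70% response, if non-responders average 2.53 or less). Where the study falls in that range cannot be judged from these documents, which also do not show that non-responders would rate the intervention lower.

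In the report, it would be sensible to print the intervention-arm mean with its 95% interval and the response rate beside the threshold. The tipping score is an optional illustration for the missing-data discussion. This conclusion assumes that the missing-data description in section 9.5 will give the number of intervention-arm women who answered the acceptability items, which is its natural reading.

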## 9.3 Analysis of Secondary Outcomes

Secondary maternal and neonatal outcomes will be analysed descriptively and exploratorily. Continuous variables (e.g., birth weight, gestational age, self-care agency scores) will be summarised using means and standard deviations or medians and interquartile ranges, depending on distribution. Binary outcomes (e.g., large for gestational age, preterm birth) will be summarised as proportions.

For exploratory comparisons between intervention and control groups, regression models will be used where appropriate. Logistic regression will be applied to binary outcomes, and linear regression to continuous outcomes. Effect estimates will be presented as odds ratios or mean differences with 95% confidence intervals. No adjustment for multiple comparisons will be performed.

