## 2. Study Objectives

The primary objective of VALID-II is to evaluate the feasibility of a co-created self-care and informal support intervention for women diagnosed with GDM. Feasibility is defined as the extent to which the intervention can be successfully delivered and maintained under real-world conditions and is assessed through recruitment, retention, and acceptability.

Secondary objectives are exploratory and aim to assess the potential effects of the intervention on selected maternal and neonatal health outcomes, including self-care agency, perceived social support, breastfeeding practices, pregnancy outcomes, and neonatal morbidity. These analyses are intended to generate preliminary estimates of effect size and variance to inform the design of a future definitive trial.

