#### 5. Study Population

Pregnant women attending antenatal care at the study sites are eligible for screening. Women are eligible for inclusion if they are  $\leq 28$  weeks' gestation at enrolment, reside in Thai Binh Province, are able to read and speak Vietnamese, and provide written informed consent. Both singleton and multiple pregnancies are eligible, and a history of GDM in a prior pregnancy does not preclude participation.

Women are excluded if they have known pregestational diabetes (type 1 or type 2) or severe chronic disease that would substantially interfere with pregnancy management or study participation.

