## 6. Recruitment and Study Procedures

At the first antenatal care visit, eligible women are informed about the study by trained study nurses or midwives. After providing written informed consent, participants complete a baseline questionnaire and are scheduled for a standard 75-g oral glucose tolerance test (OGTT) at gestational age 24–28 weeks.

OGTT procedures follow WHO and IADPSG diagnostic criteria. Women diagnosed with GDM are invited to participate in follow-up data collection and allocated to either the control or intervention group depending on study phase. Women without GDM continue routine care but contribute delivery and neonatal outcome data via medical records.

Women diagnosed with GDM complete additional questionnaires during pregnancy (32–40 weeks gestation) and at 8–12 weeks postpartum. Delivery and neonatal outcomes are abstracted from medical records.

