## 9.4 Adjustment for Confounding

Because the study uses a non-randomised design, baseline characteristics will be examined for imbalance between groups. If clinically relevant imbalances are observed, adjusted analyses will be conducted including key covariates such as maternal age, body mass index, parity, and gestational age at diagnosis. Adjusted analyses are considered exploratory and intended to inform future trial design rather than establish causal inference.

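### Multiple pregnancies are eligible, but plurality can enter the linear birth-outcome models only through an undefined imbalance trigger; always including it would modestly improve precision on average.

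*Combined protocol and SAP*

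**What the plan says.** Section 5 sets eligibility: "Both singleton and multiple pregnancies are eligible, and a history of GDM in a prior pregnancy does not preclude participation". Section 8 lists neonatal outcomes that include "birth weight, gestational age, large for gestational age, macrosomia, neonatal hypoglycaemia", and section 6 gives their source: "Delivery and neonatal outcomes are abstracted from medical records".

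For the exploratory comparison of the arms, section 9.3 states: "Logistic regression will be applied to binary outcomes, and linear regression to continuous outcomes". It cites birth weight and gestational age as examples of continuous variables and names no covariate.

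Section 9.4 is the only route by which covariates enter: "If clinically relevant imbalances are observed, adjusted analyses will be conducted including key covariates such as maternal age, body mass index, parity", with gestational age at diagnosis completing the examples. It does not say how an imbalance is measured or how large it must be. The list is open, so plurality could be added, but it is not named.

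No section restricts birth outcomes to singletons, stratifies by plurality, or says whether the record for an infant outcome is the woman or the infant. Section 8 points to a published protocol, not supplied here, which may settle the unit.

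**The concern.** Plurality adds variance to birth weight whether or not the arms are balanced on it. An imbalance trigger therefore asks the wrong question for a prognostic factor of this kind: the default leaves it out, and whether it gets in depends on a rule that has not been written down.

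What is at stake is the quality of the estimates. Section 9.1 says "Emphasis will be placed on estimation, confidence intervals, and clinical plausibility rather than statistical significance alone", and section 2 says of the secondary analyses: "These analyses are intended to generate preliminary estimates of effect size and variance to inform the design of a future definitive trial". A noisier difference, and an SD that mixes singletons and multiples without saying so, are weaker inputs to that future trial.

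**Working it through.** **Plan's own figure.** There is none to reproduce. The documents give no sample size, SD, share of multiples or expected difference.

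**Assumptions (none from the documents).** n = 50 or 100 women per arm, equal arms; share of twin pregnancies p = 1% to 5%, the same in both arms; singleton-twin birth weight gap D = 800 g; SD within plurality s = 450 g; no true effect.

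**Step 1: one record per woman.** The share of outcome variance explained by plurality is R² = p(1−p)D² / [s² + p(1−p)D²], and the ratio of standard errors, with to without the term, is √(1−R²).

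- p = 1%: 0.0099 × 640,000 = 6,336; R² = 6,336 / 208,836 = 0.030; ratio 0.985.
- p = 5%: 0.0475 × 640,000 = 30,400; R² = 30,400 / 232,900 = 0.131; ratio 0.932.

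Simulation (4,000 replicates per setting) agrees with the formula. The last two columns are binomial: with q = (1−p)^n, no multiples at all has probability q², and multiples in one arm only has probability 2q(1−q).

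| n per arm | p | SE ratio | Mean 95% CI width, g, without / with plurality | No multiples | Multiples in one arm only |
|---|---|---|---|---|---|
| 50 | 1% | 0.985 | 362 / 358 | 37% | 48% |
| 50 | 2% | 0.970 | 367 / 358 | 13% | 46% |
| 50 | 5% | 0.932 | 381 / 357 | 0.6% | 14% |
| 100 | 1% | 0.985 | 254 / 251 | 13% | 46% |
| 100 | 2% | 0.970 | 258 / 251 | 1.8% | 23% |
| 100 | 5% | 0.932 | 269 / 251 | <0.1% | 1% |

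The gain is about 1% to 7%. Widening the inputs to p = 0.5% with D = 500 g, and p = 5% with D = 1,000 g, gives ratios of 0.997 and 0.900. Coverage without the term is 94.9% to 95.3%, so only precision is lost. The gain is an average: at 50 per arm and 1% twins the adjusted interval is strictly narrower in 47% of samples; at 50 per arm and 5% it is narrower in 95%.

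**Step 2: one record per infant.** With a within-pair correlation of 0.6 (assumed; 20,000 replicates per setting), the plain model covers 92.3% to 94.5%. Adding plurality lowers the sampling SD by 5% to 18%. Coverage is then 94.1% to 95.2%, or 94.7% to 95.3% with standard errors clustered by mother.

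**Step 3: the trigger.** Also at infant level, three readings of the 9.4 rule were tried. Requiring Fisher p < 0.05 admits plurality in 0% to 2% of replicates, a standardised difference above 0.25 in 1% to 24%, and one above 0.1 in 49% to 67%. The sampling SD exceeds that of the always-included model by 5% to 19%, 3% to 15% and 0% to 2% respectively. The model that is fitted depends on which reading is chosen.

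**Step 4: gestational age.** Per pregnancy, with g the gap in SD units, the reduction is 1 − 1/√(1 + p(1−p)g²). For an assumed g of 1 to 2 it runs from 0.5% (p = 1%, g = 1) to 8% (p = 5%, g = 2).

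**Step 5: cost.** If plurality had no effect at all, a term with 3% prevalence would widen the interval by 0.7% at 30 per arm, 0.5% at 50 and 0.3% at 100.

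**Step 6: planning variance.** With one record per woman, the all-births variance exceeds the within-plurality variance by 6,336 / 202,500 = 3% (p = 1%) to 30,400 / 202,500 = 15% (p = 5%).

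**The case against.** **The larger figures depend on a unit that the plan does not state.** Section 9.1 says "all participants are analysed in the group to which they were allocated based on study phase", and participants are women. On that reading coverage is nominal and the gain is 1% to 7%. This stands. A reader might infer that the planned intervals are too narrow; the documents do not support that, because it holds only if infants are the rows and plurality is left out.

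**The trigger may work.** The rule concerns clinical relevance, so a significance test is a poor reading of it. With a standardised difference above 0.1 almost nothing is lost, and the open list lets plurality in. This stands as a possibility, but the plan commits to neither.

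**The term can amount to dropping multiples.** When all multiples fall in one arm, the adjusted contrast equals the singleton-only contrast. On these inputs that happens in about 1% to 48% of samples. It is a real limit and should be stated.

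**A reader might infer bias.** A split of 1 in 50 against 3 in 50 moves the unadjusted difference by 800 × 2/50 = 32 g. If the chance of a multiple is the same in both phases, such shifts are variance, not bias. That equality is itself assumed, since the arms are sequential and non-randomised. Confounding by phase is a separate and larger issue that this term does not resolve.

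**A reader might extend the term to the binary outcomes or to gestational weight gain.** In penalised logistic fits on assumed event rates, it changed the SD of the log odds ratio by −0.5% to +7.5%, which is no gain, and the odds ratio becomes conditional on plurality. In unpenalised fits the plurality coefficient was often infinite. For gestational weight gain, the documents give no basis for a gap.

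**Conclusion.** The point holds in a limited form. Multiples are eligible, the linear models carry no covariate by default, and plurality can enter only through an undefined rule that does not name it. Always including it is the better choice for birth weight and gestational age.

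The size is modest: about 1% to 7% off the sampling SD of the birth weight difference with one record per woman, or about 5% to 18% with infants as rows, where it also repairs most of the undercoverage. Every input is assumed, and in samples with no multiples the term changes nothing. The affected outcomes are exploratory, and recruitment, retention and acceptability are untouched. It is worth considering because it costs little, not because the plan fails without it.

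**What to change.** State in section 9.3 that:

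1. plurality is always a covariate in the linear models for birth weight and gestational age, regardless of the 9.4 trigger;
2. gestational age is analysed per pregnancy;
3. if birth weight is analysed per infant, standard errors are clustered by mother;
4. the number of multiples is reported by arm, together with the birth weight SD for all births and for singletons, so that the future trial can use the one that matches its eligibility.

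The cost is SAP wording, one degree of freedom (under 1% of interval width from 30 per arm), and a check that plurality is captured. That check should confirm that the value reflects what was known at GDM diagnosis, since delivery records show plurality at birth. The report should say so when all multiples fall in one arm, because the contrast is then the singleton-only one. The wording should be settled before outcomes are compared; section 11 describes the trial as ongoing.

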## 9.4 Adjustment for Confounding

Because the study uses a non-randomised design, baseline characteristics will be examined for imbalance between groups. If clinically relevant imbalances are observed, adjusted analyses will be conducted including key covariates such as maternal age, body mass index, parity, and gestational age at diagnosis. Adjusted analyses are considered exploratory and intended to inform future trial design rather than establish causal inference.

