## 3. Study Design

VALID-II is a two-arm, non-randomised feasibility intervention study with a delayed intervention design. The study is conducted in two sequential phases rather than in parallel.

In the first phase, women diagnosed with GDM are allocated to a control group and receive standard care. During this phase, a subgroup of women and their informal support persons participate in an embedded ethnographic study. Findings from this qualitative work inform the co-creation of the intervention.

In the second phase, after a delay of approximately three months, a new group of women diagnosed with GDM is allocated to the intervention arm and receives the co-created intervention in addition to standard care. This delayed design was chosen to allow meaningful intervention development grounded in participants' lived experiences and to ensure cultural relevance.

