#### 4. Study Setting

The study is conducted in Thai Binh Province, northern Vietnam. Participants are recruited from two health facilities: Thai Binh Maternity Hospital, a public hospital providing antenatal care and delivery services, and Kim Ngan Clinic, a private clinic providing antenatal care only. Both facilities serve urban and peri-urban populations and routinely perform oral glucose tolerance testing during pregnancy.

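### Section 9.4 adjusts the secondary comparisons only if an undefined imbalance is seen, although arm is set by study phase; report an adjusted estimate from a fixed covariate set every time

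*Combined protocol and SAP*

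**What the plan says.** Section 3 describes the design: "The study is conducted in two sequential phases rather than in parallel". The second phase enrols new women after a gap of about three months. Section 6 confirms that women with GDM are "allocated to either the control or intervention group depending on study phase", and section 9.1 analyses them in those groups.

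Section 9.4 acknowledges that the design is non-randomised and has baseline characteristics examined. It then states: "If clinically relevant imbalances are observed, adjusted analyses will be conducted including key covariates such as maternal age, body mass index, parity". Gestational age at diagnosis completes the list of examples. Section 9.3 names the models ("Logistic regression will be applied to binary outcomes, and linear regression to continuous outcomes") but no covariates.

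Three other places bear on the point:

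- Section 4 lists two recruiting facilities of different kinds: a public hospital that also handles deliveries, and "a private clinic providing antenatal care only".
- Section 2 gives the secondary comparisons a purpose: "These analyses are intended to generate preliminary estimates of effect size and variance to inform the design of a future definitive trial".
- Section 9.5 says "no formal imputation of missing data is planned".

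No section commits to an adjusted estimate irrespective of what the baseline table shows.

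**The concern.** When arm and phase coincide, confounding has to be planned for. Section 9.4 makes adjustment depend on inspecting the data and does not say what size of difference counts, on what scale, or for which covariates. Two consequences follow.

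First, imbalance that falls below whatever threshold is later applied stays in the reported effect. An imbalance too small to be called relevant can still bias the estimate if the covariate predicts the outcome.

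Second, the trigger and the covariate set can both be settled after the data are known. The same sentence permits an adjusted analysis with four covariates, one with more, or none.

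At stake are the preliminary effect sizes handed to the definitive trial. Section 9.1 puts the emphasis on estimation, so bias in the estimate is the relevant harm.

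**Working it through.** **Is there a figure to reproduce?** No. The documents give no sample size, SD, event rate, site mix or expected imbalance for these comparisons. Everything below is an illustration on assumed inputs.

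**Assumptions.** Continuous outcome with SD 1 and no true effect; n = 50 or 100 women per arm; one covariate with true shift δ = 0.2 or 0.3 SD between phases and correlation ρ = 0.5 or 0.6 with the outcome; adjustment only if the observed standardised difference d exceeds c in absolute value, with c = 0.1, 0.25 or 0.5.

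**Step 1, no adjustment.** Bias = ρδ, from 0.5 × 0.2 = 0.10 to 0.6 × 0.3 = 0.18 SD.

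**Step 2, conditional adjustment on one covariate.** The adjusted estimate is unbiased, so bias comes only from samples in which the trigger does not fire:

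bias = ρ·E[d; |d| ≤ c] = ρ{δ[Φ(u) − Φ(l)] − s[φ(u) − φ(l)]}

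with s ≈ √(2/n), u = (c − δ)/s and l = (−c − δ)/s.

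Worked case: n = 100, δ = 0.3, ρ = 0.5, so s = 0.1414.

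- c = 0.25: u = −0.354, l = −3.889. Bias = 0.5 × [0.3 × (0.3618 − 0.0001) − 0.1414 × (0.3748 − 0.0002)] = 0.028.
- c = 0.5: u = 1.414, l = −5.657. Bias = 0.5 × [0.3 × 0.9214 − 0.1414 × 0.1468] = 0.128.
- c = 0.1: the same formula gives 0.002.

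The trigger fires with probability 92%, 64% and 8% at c = 0.1, 0.25 and 0.5. A simulation of this case (3,000 runs) gave 93%, 64% and 8%, bias of 0.003, 0.029 and 0.126 SD, and false-positive rates of 4.6%, 5.5% and 13.8%. Never adjusting gave 17.6-19.5%; always adjusting gave 4.3-5.2%. At n = 200 per arm the three thresholds gave 4.7%, 8.2% and 30.0%.

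**Step 3, closer to the text.** Four covariates are examined, and all four enter the model if any one exceeds c. Simulation used 12,000 replicates per cell, n = 50 or 100. Ranges are bias in SD, with coverage of the 95% interval in brackets.

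| Scenario | Never adjust | c = 0.1 | c = 0.25 | c = 0.5 |
|---|---|---|---|---|
| One covariate, triggering on itself | 0.10-0.18 | 0.001-0.005 | 0.02-0.05 (94-97%) | 0.08-0.15 (81-94%) |
| Four examined, one shifted | 0.10-0.18 | at most 0.002 | 0.011-0.034 (94-96%) | 0.078-0.156 (80-94%) |
| Four examined, all shifted 0.1-0.2 SD, multiple correlation R = 0.5-0.6 | 0.10-0.24 | – | 0.006-0.042 (94-96%) | 0.08-0.22 (66-93%) |

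In the second row the trigger fires in 50-81% of samples at c = 0.25 and in 2-20% at c = 0.5. The unadjusted range in the third row follows from equal coefficients R/2 on four covariates: 4 × (R/2) × δ = 2Rδ, from 2 × 0.5 × 0.1 = 0.10 to 2 × 0.6 × 0.2 = 0.24.

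**Step 4, always adjusting.** With five covariates (four continuous plus binary site), bias was at most 0.003 SD and coverage 94.6-95.3%. This holds only for covariates that are in the model and measured without error.

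**Binary outcomes.** With a true odds ratio of 1, a covariate odds ratio of 1.5-2.0 per SD and about 20-44 events, the median odds ratio was 1.10-1.23 unadjusted and 0.99-1.02 with the five covariates.

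**Site.** No figure can be given, because the documents report neither the site mix by phase nor any difference between sites.

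**The case against.** The strongest reply is that material harm appears only if the trigger is read as about half an SD, and nothing in the plan suggests so lax a reading. At 0.1 the rule is practically the same as always adjusting, and at 0.25 coverage stays at 94-97% with 50-100 women per arm. This stands as a limit on size. It does not rescue the rule, because the plan chooses none of these readings, and at 200 women per arm even 0.25 gave 8.2% false positives.

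The assumed shift of 0.2-0.3 SD is also not drawn from the documents. Both phases use the same facilities, eligibility criteria and 24-28 week OGTT window, which limits variation in gestational age at diagnosis. That is fair: imbalance is possible and should be planned for, but its size is unknown.

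The comparisons are labelled exploratory and non-causal, and no covariate set can separate arm from calendar period. Both are true. They cap the seriousness of the point and require a stated limitation, but do not justify leaving measured case mix to discretion.

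The open list in section 9.4 does not exclude site. Correct: the complaint is lack of commitment, and the case for site rests on the difference in facility type alone.

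Finally, rare outcomes may not support five covariates. That is a real cost, set out with the fix.

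**Conclusion.** The concern holds. Section 9.4 makes adjustment contingent on an undefined reading of the observed data, with an open covariate list, in a design where arm equals phase. On the assumed inputs, the bias left in a continuous outcome is negligible at a 0.1 SD trigger, small at 0.25 (about 0.01-0.05 SD) and material at 0.5 (about 0.08-0.22 SD, coverage as low as 66%). The defect is that the plan permits all three, not that large bias is certain. It affects only the exploratory secondary comparisons; recruitment, retention, acceptability and the progression criterion are untouched. The change should be made. Confidence is medium, because every numerical input is assumed.

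**What to change.** In section 9.4, delete the condition on observed imbalance. For every between-group secondary comparison, report an adjusted estimate beside the unadjusted one, whatever the baseline table shows. Use one fixed set: maternal age, BMI, parity, gestational age at diagnosis and recruiting site. Add the baseline value of the outcome where it was collected; section 6 says only that "participants complete a baseline questionnaire", so the SAP should list the outcomes to which this applies. Keep the linear and logistic models of section 9.3. Report the number of women in each model and, for binary outcomes, the number of events. Interpret adjusted odds ratios cautiously where events are few, and say so where a model cannot be estimated. State that adjustment cannot remove calendar-period confounding.

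This is a wording change: four covariates are already named and the two facilities are known. Section 9.1 has the SAP finalised before intervention-group data collection ends, and section 11 describes the trial as ongoing. The analytical costs, on assumed inputs, are:

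- **Continuous outcomes:** the standard error rises 1-4% if no covariate predicts the outcome, and falls 10-19% at a correlation of 0.5-0.6.
- **Binary outcomes:** the standard error of the log odds ratio rises 4-11% at about 20-44 events. The model cannot be estimated in 0.6-2% of runs at about 10-12 events (unadjusted 0.4-0.9%) and in 15-21% at about 5-6 events (unadjusted 9-13%). Adjusted and unadjusted odds ratios can also differ without any confounding, so the SAP should say that a gap between them is not in itself evidence of bias.
- **Missing covariates:** without imputation, if each of k covariates is missing independently in a fraction m of women, the adjusted model loses 1 − (1 − m)^k. With k = 5 and m = 1%, 2% or 5%, that is 4.9%, 9.6% or 22.6%. With a baseline outcome value as a sixth covariate it is 5.9%, 11.4% or 26.5%.

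The unadjusted estimate remains in the report throughout.
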